11.0 STATISTICAL CONSIDERATIONS

11.1 Sample size

We will test the hypothesis that only 20% of patients on either arm of the study will have undetectable PSA at 32 weeks, versus the alternative that 40% of arm B patients will. An initial cohort of 39 patients and, if continued, a second cohort of 27 patients will be randomized 2:1 to arms B and A respectively.

After stratification for prior therapy we will randomize, 2:1, nominally 13 patients to arm A and 26 patients to arm B. Because of post stratification randomization, the exact numbers in the two arms may vary slightly from 13 and 26, but the total patient number in the the initial cohort will be exactly 39 and the final sample number be exactly 66. Our intent is to compare the proportions of patients with undetectable PSA at 32 weeks. This is most simply described by the difference $(E1/26) - (C1/13)$, where C1 and E1 are the numbers of undetectable PSAs in arms A and B respectively. The cut point for continuation of the trial past the first cohort requires that

$(E1/26) - (C1/13) > -2/13 = -0.1538462\dots$. To avoid confusion due to round off of such fractions, we identify the decision boundary by $13 E1 - 26 C1 > -52$, exactly equivalent the first expression, and obtained by multiplying all terms by $13*26$.

If $13 E1 - 26 C1$ exceeds -52 AND $E1$ is at least 6 then we will randomize an additional 9 patients to arm A and 18 patients to arm B. Otherwise the study will be terminated and the null hypothesis accepted. Letting $C2$ and $E2$ be the numbers of undetectable PSAs in the second cohort, we will finally reject the null hypothesis if $22(E1 + E2) - 44(C1 + C2)$ is at least 88 and $E1 + E2$ is at least 14. The initial cohort will consist of 39 and the final cohort of 27 patients for a total of 66 patients. If the true null is 20% undetectable PSAs type I error will be 3.24% and power will be 80.3%. In this case the chance of early stopping under the null will be 60% but will be 3.23% if the true arm B fraction of undetectable PSAs is 40%.

If the null (arm A) fraction undetectable PSAs is 25% type I error increases to 10.9% and power increases to 83.3% if the arm B fraction undetectable is 45% (20% higher). If the null fraction is 30% type I error increases to 19.7% and power to 83.2% (arm B 50%, 20% higher).

The above discussion is based on the exact 2:1 split in the combined strata. This may not occur so the table below describes the decision boundaries for all possible outcomes of the split. In all cases study power is at least 80% and type I error is less than 5%. Type I error when the null fraction is 30% is always under 20%. To use the table we compute $nc1 E1 - ne1 C1$ where $nc1$ and $ne1$ are the actual numbers of arm A and arm B respectively in the initial cohort of 39. If this number, $nc1 E1 - ne1 C1 > -a1$, and $E1 > m1$ in the table, then the trial may be continued past the initial cohort. Otherwise it is terminated and the null hypothesis accepted. If the second cohort is recruited, then $nc2(E1+E2) - ne2(C1+C2)$ must be computed. $nc2$ and $ne2$ are the total numbers of patients in arms A and B respectively. If $nc2(E1+E2) - ne2(C1+C2)$ is at least r and $E1+E2$ is at least $m2$ in the table, then the null hypothesis will be rejected. The table is indexed by $nc1$ and $nc2$ only. This is so because $nc1+ne1 = 39$ invariably as does $nc2+ne2 = 66$. For example, suppose $nc1 = 13$ hence $ne1 = 26$. Then if $E1 = 7$ and $C1 = 4$, $E1 > m1 = 6$ and $13 E1 - 26 C1 = 13 * 7 - 26 * 4 = 91 - 104 = -13$, and $-13 > -52$, so the second cohort would be recruited. Finally, suppose $nc2 = 22$ hence $ne2 = 44$ and suppose $E2 = 9$ and $C2 = 2$. Then $E1+E2 = 9+7=16 > m2=14$ and $22(E1+E2) - 44(C1+C2) = 22*16 - 44*6 = 352-264 = 88$ which is at least $r = 88$. In this case the null hypothesis would be rejected.

decision boundaries						
nc1	nc2	a1	m1	r	m2	
12	21	-42	6	72	14	
12	22	-42	6	88	14	
12	23	-42	6	88	13	
13	21	-52	6	72	14	
13	22	-52	6	88	14	(this row used in example above)
13	23	-52	6	88	13	
14	21	-68	6	72	14	
14	22	-68	6	88	14	
14	23	-68	6	88	13	

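### Section 11.1 holds type I error below 5% only near the assumed 20% rate, its two stage 1 conditions conflict, and no between-arm p-value or interval is planned for the primary endpoint

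*Combined protocol and SAP*

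**What the plan says.** Section 2.1 makes the primary endpoint comparative: the proportion with undetectable PSA at 32 weeks on metformin plus bicalutamide (arm B) against bicalutamide alone (arm A). Section 11.1 takes 20% in both arms as the null and 40% in arm B as the alternative. It enrols 39 patients, then 27 more, randomised 2:1. E1 and C1 are first-cohort responders in arms B and A; E2 and C2 are those of the second cohort.

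- **Stage 1, nominal split.** The between-arm statistic 13 E1 − 26 C1 must lie above −52, and a count condition is added: "AND $E1$ is at least 6 then we will randomize an additional 9 patients to arm A and 18 patients to arm B".
- **Stage 1, table paragraph.** The between-arm condition is paired with a different count condition: "and $E1 > m1$ in the table, then the trial may be continued past the initial cohort". The table gives m1 = 6 in every row.
- **Final rule, nominal split.** The null is rejected if 22(E1+E2) − 44(C1+C2) "is at least 88 and $E1 + E2$ is at least 14".
- **Stated performance.** "If the true null is 20% undetectable PSAs type I error will be 3.24% and power will be 80.3" per cent, with early stopping of 60% under the null and 3.23% under the alternative. The claim made for every row of the table is: "In all cases study power is at least 80% and type I error is less than 5" per cent.
- **Disclosed sensitivity.** "If the null (arm A) fraction undetectable PSAs is 25% type I error increases to 10.9" per cent, then 19.7% at 30%. For all splits: "Type I error when the null fraction is 30% is always under 20" per cent. No figure is given above 30%.
- **Worked example.** With 16/44 against 6/22: "In this case the null hypothesis would be rejected".

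Fisher's exact test appears in section 11.3 for a secondary PSA endpoint only. Section 1.2 reports the trial of bicalutamide 50 mg in biochemical recurrence as still pending.

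**The concern.** Three things limit what a reader can take from a boundary crossing.

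First, the error statement carries no condition on the control rate, although the rule's error climbs quickly once the common rate leaves 20%. The documents give no undetectable-PSA rate for bicalutamide 50 mg in this population, so they do not show that 20% is right.

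Second, section 11.1 gives two stage 1 conditions that disagree when E1 is exactly 6, and the power claim sits beside the one that does not deliver it. With 6 responders in arm B and 4 or fewer in arm A (13×6 − 26×4 = −26, which exceeds −52), one paragraph continues the trial and the other stops it.

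Third, the final between-arm requirement is an observed difference of only 88/(22×44) = 9.1 percentage points. With no p-value or interval planned, a report of a rejected null would not show how strong the randomised comparison is.

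**Working it through.** **Inputs (section 11.1).** Arm A 13 then 9; arm B 26 then 18; the rules above; null 20%/20%; alternative 20%/40%. For the other table rows I used the tabled a1 as the signed bound, as the worked example does with −52.

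**Method.** Exact enumeration with independent binomials:

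P(reject) = Σ b(C1;13,pA) · b(E1;26,pB) · b(C2;9,pA) · b(E2;18,pB), summed over outcomes that pass stage 1 and meet the final rule.

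**Step 1: reproduce the plan (nominal split, E1 at least 6).**

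| Quantity | Stated | Exact |
|---|---|---|
| Type I error, 20% | 3.24% | 3.25% |
| Power, 20% vs 40% | 80.3% | 80.4% |
| Early stopping, null | 60% | 60.0% |
| Early stopping, alternative | 3.23% | 3.24% |
| Type I error, 25% | 10.9% | 11.0% |
| Type I error, 30% | 19.7% | 19.7% |

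The plan's figures reproduce; the small gaps fit truncation rather than rounding.

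**Step 2: type I error by common rate (E1 at least 6).**

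| Common rate | Nominal split | Range over nine rows |
|---|---|---|
| 20% | 3.25% | 3.2-4.4% |
| 25% | 11.0% | 10.9-11.7% |
| 30% | 19.7% | 18.5-19.8% |
| 35% (assumed) | 24.7% | 22.9-25.0% |
| 40% (assumed) | 26.5% | 24.7-27.6% |

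Solving for 5% gives a common rate of 21.4% (20.5-21.5% over rows).

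**Step 3: the two stage 1 conditions.**

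| | E1 at least 6 | E1 more than 6 |
|---|---|---|
| Power, nine rows | 80.0-80.9% | 78.2-79.7% in eight, 80.0% in one |
| Type I error at 20%, nine rows | 3.2-4.4% | 2.9-4.2% |
| Early stopping, nominal, null | 60.0% | 75.4% |
| Early stopping, nominal, alternative | 3.2% | 6.3% |

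Of the two, only the at-least-6 condition matches the stated 3.24%, 80.3%, 60% and 3.23%.

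**Step 4: between-arm evidence at a crossing (E1 at least 6).** The one-sided Fisher p is the hypergeometric upper tail.

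- Worked example: 16/44 − 6/22 = 36.4% − 27.3% = 9.1 points. The statistic is 22×16 − 44×6 = 88, exactly on the boundary. One-sided Fisher p = 0.33; Newcombe 95% interval −15.3 to +29.5 points.
- How typical that is: when 20% vs 40% is true, 5% of crossings (nominal split) lie on the difference boundary, and the median one-sided p of all crossings is 0.056.
- Share of crossings with p above 0.10, over rows: 33-35% when 20% vs 40% is true, 54-62% under a 20% null, 72-74% under a 30% null.

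The 0.10 benchmark is borrowed from section 11.3, where it applies to a secondary endpoint; reading it as one-sided is my inference.

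**The case against.** The strongest reply is that the plan hides nothing. Section 11.1 names the 20% null, gives the error at 25% and 30%, and follows the less-than-5% sentence directly with the 30% figure. That stands. A reader might infer that the sentence is false or that the inflation is concealed; the documents support neither. What is missing is the condition in the sentence and the figures above 30%.

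A reader might also infer that the rule is really a single-arm test and the control arm is decorative. Near 20% the arm B counts do most of the work: E1 at least 6 and a total of at least 14, ignoring arm A, give 4.3% against 3.25% for the full rule. At 30% the same arm B counts give 44.6% against 19.7%, so there the concurrent control matters a great deal. The single-arm reading fails away from 20%.

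The worked example illustrates how to use the table and is a boundary case, so its p of 0.33 must not stand for crossings in general.

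Fisher's test is a demanding yardstick. After stage 1, the chance of p at or below 0.10 under a common rate is only 4.1% at 20% and 6.5% at 40%, so part of the one-third figure reflects its conservatism.

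Finally, the discrepancy over E1 may be loose notation, and it costs at most about two points of power. But at E1 = 6 it can decide whether the trial continues, so it needs settling whatever its origin.

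**Conclusion.** The concern holds as a matter of wording, internal consistency and reporting. The design's stated calculations are correct under the at-least-6 condition.

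- Error below 5% is secured only up to a common rate of about 21.4%. The undisclosed range adds about 25% at 35% and 27% at 40%. Those two rates are assumptions. The 40-77% undetectable-PSA rates in section 1.2 come from finasteride plus flutamide and cannot stand in for this control arm.
- The power claim of at least 80% fails in eight of nine rows under the table paragraph's own stage 1 condition. Nominal early stopping becomes 75.4%/6.3% rather than the stated 60%/3.23%.
- The randomised primary comparison has a decision rule but no planned p-value or interval. About a third of crossings would carry a one-sided Fisher p above 0.10 even when the design alternative is true.

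It is tempting to add that the plan wrongly claims superiority from a crossing. Section 11.1 speaks only of rejecting the null and makes no such claim, so a disclaimer would be optional wording.

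The figures assume independent binomial outcomes with all planned patients evaluable.

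**What to change.** Keep the 39 + 27 patients and the boundary, and make three changes.

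1. **Stage 1 condition.** Reconcile the two paragraphs of section 11.1 so that one condition on E1 applies throughout. The stated operating figures reproduce with at least 6. If more than 6 is intended, restate power, type I error and early stopping.
2. **Error statement.** Tie it to its rate, for example: at a common rate of 20%, type I error is below 5% for every split. Add 24.7% at 35% and 26.5% at 40% (nominal split).
3. **Reporting.** With the boundary decision, give a one-sided Fisher exact p-value and a 95% confidence interval for the difference between arms. State that neither is adjusted for the two-stage design and that Fisher's test is conservative.

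The cost is a few sentences and two statistics. The downside is that some crossings will be published beside weak between-arm evidence, and the plan should expect this: a one-sided 10% Fisher test after the stage 1 rule has about 54% power for 20% vs 40%, against 80% for the boundary. Calling a crossing a go/no-go signal is optional.

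### The interim stop/go rule is printed in conflicting forms, and the form printed with the decision table does not give the stated 80% power

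*Combined protocol and SAP*

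**What the plan says.** All of this is in section 11.1, Sample size.

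- **Hypotheses and size.** The null is 20% undetectable PSA at 32 weeks in both arms, "versus the alternative that 40% of arm B patients will". The cohorts are described as follows: "An initial cohort of 39 patients and, if continued, a second cohort of 27 patients will be randomized 2:1 to arms B and A respectively".
- **Interim rule, main text (nominal 13/26 split).** "If $13 E1 - 26 C1$ exceeds -52 AND $E1$ is at least 6 then we will randomize an additional 9 patients"; those nine are for arm A, with eighteen more for arm B. Otherwise the study ends and the null is accepted.
- **Interim rule, table text (any realised split).** "If this number, $nc1 E1 - ne1 C1 > -a1$, and $E1 > m1$ in the table", the trial may go on; otherwise it ends and the null is accepted. The table lists a1 as -42, -52 or -68, and m1 as 6 in all nine rows.
- **Worked example.** With E1 = 7 and C1 = 4 it writes E1 > m1 = 6, obtains a difference of -13, and concludes: "and $-13 > -52$, so the second cohort would be recruited".
- **Claimed properties.** At the nominal split: type I error 3.24%, power 80.3%, early stopping 60% under the null and 3.23% under the alternative. Over all splits: "In all cases study power is at least 80% and type I error is less than 5" per cent.

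**The concern.** There are two separate conflicts. First, at exactly six arm B responders the main text continues (if the difference condition is met), while the table text terminates and accepts the null. Second, because a1 is tabulated with its minus sign, comparing with -a1 sets the nominal boundary at +52, whereas the main text and the example both use -52.

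This rule decides whether the primary question is carried forward, and six responders is a plausible interim result. If the conflict is first noticed when E1 = 6 has been observed, the choice between the two forms is made with the outcome in view, and the two-stage test is no longer fully pre-specified. The power guarantee printed next to the table also needs to be true of the rule printed there.

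**Working it through.** **Inputs, all from section 11.1.** Response rates: 20%/20% (null) and 20% in A, 40% in B (alternative). Cohort 1 is 39 patients and the total is 66. Boundaries come from the nine table rows; the nominal row is nc1 = 13, nc2 = 22, a1 = -52, m1 = 6, r = 88, m2 = 14. The final rule rejects if nc2(E1+E2) - ne2(C1+C2) ≥ r and E1+E2 ≥ m2.

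**Method.** C1, E1, C2 and E2 are independent binomials. P(stop) is the sum of P(C1)P(E1) over all pairs that fail the interim rule. P(reject) is the sum of P(C1)P(E1)P(C2)P(E2) over all outcomes that pass both stages. The enumeration is exact.

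**Step 1. Reproduce the plan's figures.** Nominal row, with E1 ≥ 6 and difference > -52:

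| Quantity | Plan | Recomputed |
|---|---|---|
| Type I error (20%) | 3.24% | 3.246% |
| Power (20% v 40%) | 80.3% | 80.36% |
| Early stop, null | 60% | 60.05% |
| Early stop, alternative | 3.23% | 3.236% |
| Type I error / power (25%, 25% v 45%) | 10.9% / 83.3% | 10.98% / 83.38% |
| Type I error / power (30%, 30% v 50%) | 19.7% / 83.2% | 19.70% / 83.25% |

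Every figure agrees when cut off at the printed digit.

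**Step 2. Same row, with E1 > 6 and difference > -52.** Type I error 3.04%, power 79.2%, early stop 75.4% (null) and 6.34% (alternative). These do not match the plan.

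**Step 3. Same row, fully literal: E1 > 6 and difference > +52.** Type I error 1.66%, power 55.0%, early stop 92.3% (null) and 42.0% (alternative). The example's own value is 13×7 - 26×4 = 91 - 104 = -13. It exceeds -52 but not +52, so the literal formula would stop the trial that the example continues.

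**Step 4. Power (%) at 20% v 40% in all nine rows.**

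| nc1, nc2 | E1 ≥ 6, > a1 | E1 > 6, > a1 | E1 > 6, > -a1 |
|---|---|---|---|
| 12, 21 | 80.85 | 80.03 | 62.1 |
| 12, 22 | 80.45 | 79.72 | 61.7 |
| 12, 23 | 80.34 | 79.55 | 62.1 |
| 13, 21 | 80.73 | 79.47 | 55.4 |
| 13, 22 | 80.36 | 79.22 | 55.0 |
| 13, 23 | 80.23 | 79.00 | 55.4 |
| 14, 21 | 80.50 | 78.58 | 48.5 |
| 14, 22 | 80.17 | 78.38 | 48.2 |
| 14, 23 | 80.02 | 78.15 | 48.6 |

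The first column satisfies the guarantee in every row. The second satisfies it only in the first row, and the loss against the first column is 0.7 to 1.9 points. Type I error at 20% is 3.20 to 4.41% in the first column and lower in the other two.

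**Step 5. How often the two E1 thresholds disagree.** At the nominal split with E1 = 6, the difference condition is 13×6 - 26×C1 > -52, so C1 < 130/26 = 5, that is C1 ≤ 4.

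- P(E1 = 6 | n = 26) is 0.170 at 20% and 0.0345 at 40%.
- P(C1 ≤ 4 | n = 13, 20%) is 0.901.
- Null: 0.170 × 0.901 = 0.153. Alternative: 0.0345 × 0.901 = 0.031.

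These equal the differences in early stopping between steps 1 and 2: 75.35 - 60.05 = 15.3 points and 6.34 - 3.24 = 3.1 points.

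**The case against.** The intended rule can be recovered from the document. The main text says in words that E1 "is at least 6 then we will randomize an additional 9 patients to arm A and 18 patients to arm B", and the printed 60% and 3.23% match that form and exclude E1 > 6. The boundary of -52 is stated in the main text and used again in the example, so the -a1 wording is recognisable as a sign slip and nobody is likely to apply +52. The example's strict inequality is weak evidence of intent: it also writes 16 > m2 = 14, where the rule is at least m2, and with E1 = 7 it cannot separate the two readings. Finally, the E1 wording alone costs less than 2 points of power, and type I error is never breached.

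Most of this stands, and it limits the size of the problem. The 48 to 62% figures describe what the literal text does, not what is likely to happen. The guarantee itself is correct for the main-text rule. What remains is that a binding threshold has two incompatible forms, nothing in the document says which governs, and the table text is the one offered for every realised split. It uses at least for r and m2 but > for m1, so a careful reader has reason to take the interim inequality as strict.

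**Conclusion.** The concern holds. The plan's calculations are sound for E1 ≥ m1 with difference > a1, but the rule printed with the table is neither of these. With E1 > 6 alone, nominal power is 79.2% instead of 80.3%, eight of nine rows miss the stated 80%, and nominal early stopping becomes 75.4% and 6.3% instead of 60% and 3.23%. Taken literally with -a1 as well, power is 48 to 62%. Only the power half of the guarantee fails; the type I error half holds on every reading.

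The correction matters because the two E1 thresholds reverse the decision in 15.3% of trials under the null and 3.1% under the alternative at the nominal split, not because the power loss is large. These results assume independent binomial responses at the plan's own rates, all 39 and 66 patients evaluable, and the final rule as stated.

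**What to change.** In the table text of section 11.1:

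1. Replace E1 > m1 with E1 ≥ m1.
2. Replace > -a1 with > a1, or keep -a1 and list the column as 42, 52 and 68.
3. In the example, write E1 = 7 ≥ m1 = 6 and, for consistency, E1+E2 = 16 ≥ m2 = 14.

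No sample size, boundary or stated operating characteristic changes. If at least seven responders is what is really intended, change the main text to match, restate the nominal early stopping as about 75% and 6.3% and the power as about 79%, and withdraw the claim of at least 80% in all cases. Either way, settle it before the interim responses are examined. If they have already been examined, record which form was applied and the values of E1 and C1. The cost is two symbols and one example line.

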11.2 Toxicity assessment

A DLT rate of 20% will be considered excessive for arm B. A rate of 5% is expected and acceptable. If 5 of the initial cohort in arm B experience DLT, the study will be halted for reassessment of dose. If 7 of arm B patients experience DLT the regimen will be considered too toxic. This set of rules has at least 80% chance of declaring arm B too toxic when the true DLT rate is 20%. This chance under the null is about 1%. The chance of halting the trial early is over 57% for a 20% DLT rate and less than 1% if this rate is only 5%.

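### The 80% chance in section 11.2 of flagging a 20% DLT rate assumes both cohorts are enrolled; allowing for the futility stop in 11.1, it is about 70% when metformin adds nothing

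*Combined protocol and SAP*

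**What the plan says.** Section 11.2 sets two reference rates: "A DLT rate of 20% will be considered excessive for arm B", and "A rate of 5% is expected and acceptable". It then gives two rules for arm B. The first applies to the first cohort: "If 5 of the initial cohort in arm B experience DLT, the study will be halted for reassessment of dose". The second applies to arm B as a whole: "If 7 of arm B patients experience DLT the regimen will be considered too toxic".

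Three operating characteristics follow:

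- Detection: "This set of rules has at least 80% chance of declaring arm B too toxic when the true DLT rate is 20" per cent.
- False alarm: "This chance under the null is about 1" per cent.
- Early halt: "The chance of halting the trial early is over 57% for a 20% DLT rate and less than 1% if this rate is only 5" per cent.

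Section 11.1 governs whether the second cohort exists. After 39 patients (nominally 13 in arm A, 26 in arm B), a further 9 and 18 are randomized only if 13·E1 − 26·C1 exceeds −52 and E1 is at least 6. Here E1 and C1 are the numbers with undetectable PSA in arms B and A. If the criterion fails, the study ends and the null is accepted. For a 20% null rate, 11.1 states: "In this case the chance of early stopping under the null will be 60" per cent. It gives 3.23% when the arm B rate is 40%.

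Section 11.2 does not mention the futility stop and does not limit its figures to trials that reach 66 patients.

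**The concern.** The toxicity rules and the futility rule run in the same trial, but 11.2 evaluates the toxicity rules as if arm B always reached 44. When metformin adds nothing, the plan expects to stop after about 26 arm B men more often than not. Fewer men are then observed, and the chance of reaching a fixed DLT count is lower.

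Safety and tolerability of metformin is a secondary endpoint in section 2.2, and 11.2 holds the stated decision rules for arm B toxicity. A reader who takes the 80% at face value will believe that a trial ending at futility without a flag had at least that chance of detecting a 20% DLT rate. Under the plan's own null, the chance was lower.

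**Working it through.** **Inputs.** From 11.2: DLT rates 20% and 5%; halt at 5 DLTs in the first arm B cohort; too toxic at 7 DLTs in arm B. From 11.1: arm B numbers 26, then 18 more (44 in all); the futility criterion; the stop probabilities of 60% and 3.23%. One assumption is not in the documents: DLT and PSA response are independent.

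**Step 1: reproduce the figures in 11.2, full enrolment.** Exact binomial tails, with X1 the DLTs in the first 26 arm B men and X2 those in the next 18:

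- 7-DLT rule alone: P(X ≥ 7 | 44, 0.20) = 0.804.
- Either rule: P(X1 ≥ 5) + Σ over x = 0 to 4 of P(X1 = x)·P(X2 ≥ 7 − x) = 0.617 + 0.210 = 0.827.
- At a 5% DLT rate: either rule 0.0118; 7-DLT rule alone 0.0059.
- Halt: P(X1 ≥ 5 | 26) = 0.617 at 20% and 0.0085 at 5%. With 25 arm B men, the smallest first cohort in the 11.1 boundary table, it is 0.579 at 20%.

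These match the stated figures of at least 80%, about 1%, over 57% and less than 1%. The false-alarm figure of about 1% fits the either-rule reading (1.18%) better than 7 DLTs alone (0.59%).

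**Step 2: first cohort only.** At a 20% DLT rate, P(X1 ≥ 5 | 26) = 0.617 and P(X1 ≥ 7 | 26) = 0.253.

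**Step 3: probability of the futility stop.** Exact enumeration of E1 ~ Bin(26) and C1 ~ Bin(13), arm A at 20%:

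- arm B 20%: 0.6005 (the plan says 60%)
- arm B 30%: 0.188
- arm B 40%: 0.0324 (the plan says 3.23%)

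**Step 4: combine.** With s the stop probability:

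- Either rule: s × 0.617 + (1 − s) × 0.827
- 7-DLT rule alone: s × 0.253 + (1 − s) × 0.804

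At arm B 20%, these are 0.6005 × 0.617 + 0.3995 × 0.827 = 0.701 and 0.6005 × 0.253 + 0.3995 × 0.804 = 0.473.

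| Situation, true DLT rate 20% | Either rule | 7-DLT rule alone |
|---|---|---|
| Both cohorts enrolled | 82.7% | 80.4% |
| Arm B 40% undetectable | 82.0% | 78.7% |
| Arm B 30% undetectable | 78.7% | 70.1% |
| Arm B 20% undetectable (no benefit) | 70.1% | 47.3% |

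The right-hand column also assumes that a trial halted at 5 or 6 DLTs resumes at the same DLT rate.

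**Step 5: sensitivity under no benefit.**

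- Across the nine splits in the 11.1 table: 66.6% to 73.6% (either rule) and 43.4% to 52.1% (7-DLT rule).
- The text introducing that table asks for E1 greater than 6 rather than at least 6. On that reading the probability of continuing falls to 0.246, and the figures are 66.8% and 38.9%.
- If a halt at 5 or 6 DLTs were permanent, the 7-DLT figure would be about 34%.
- At a 5% DLT rate, the either-rule figure with the futility stop is 0.98%, so the stated false-alarm figure stands.

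**The case against.** The strongest reply is that nothing in 11.2 is miscalculated. Every figure is correct for the toxicity rules taken alone, and the early-halt figure of over 57% already tells a reader roughly what the first cohort can deliver. The sentence refers to a set of rules, and for the set the figure survives the futility stop at the design alternative (82.0%). A futility stop also enrols no more arm B men, so no extra exposure follows from a missed flag. All of this stands. It makes the point one about an unstated condition and limits its consequence. It does not rescue an unqualified 80%, because under the plan's own null the either-rule chance is 70%.

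Two stronger readings are tempting, and the documents do not support them.

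- A reader might infer that the design has only a 47% chance of detecting excess toxicity. That requires counting the 7-DLT rule alone. The plural wording and the false-alarm figure of about 1% both favour counting either rule. It also requires a halted trial to resume with an unchanged DLT rate, which 11.2 does not say.
- A reader might infer that a trial ending after cohort 1 with 5 or 6 DLTs in 26 reaches no toxicity conclusion. At a 20% DLT rate that outcome has probability 0.617 − 0.253 = 0.364. But 5 DLTs trigger the prespecified halt, section 11.5 requires adverse events to be summarised in treated patients, and section 12.2 has the monitoring board review toxicity at least every 6 months. The real gap is narrower: 11.2 does not say whether such a result counts as too toxic, and no interval for the DLT rate is specified.

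**Conclusion.** The point holds as a missing condition on a stated operating characteristic. The 80% describes a trial that enrols both cohorts. With the futility stop included, the either-rule chance at a 20% DLT rate is essentially unchanged at the design alternative, just under 80% at an intermediate benefit (arm B 30%), and about 70% with no benefit: a shortfall of roughly 10 percentage points against the stated floor. The 7-DLT figures are lower and depend on an interpretation that the plan leaves open.

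The combined figures rest on independence of DLT and PSA response, the nominal 26 and 44 in arm B, and the futility criterion read as E1 at least 6. The alternative splits and the stricter reading of E1 move the no-benefit figure within about 67% to 74%, so the conclusion does not depend on either choice. Correlation between DLT and response could move it, and the documents give no joint model. The practical effect is on how far the toxicity finding can be relied on, not on patient exposure, so this is a correction that should be made rather than a flaw in the design.

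**What to change.** Restate the detection sentence in 11.2 along these lines: about 83% (80% for the 7-DLT rule alone) if both cohorts are enrolled; about 70% (47%) allowing for the futility stop when arm B is no better than arm A, assuming DLT and PSA response are independent. State which rule the percentage refers to, and note that the 47% also assumes a trial halted at 5 or 6 DLTs resumes at the same DLT rate. Add that, if the trial ends after cohort 1, the arm B DLT rate will be reported with an exact confidence interval.

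This is a text change only. No toxicity boundary, dose or sample size changes; the cost is a less favourable stated figure.
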